MedDO	Medical Devices Ordinance
MD	Medical Device
MDR	Medical Device Regulation (EU) 2017/745 of 5 April 2017
MKG	Mund-, Kiefer- und Gesichtschirurgie
ORIF	Open Reduction and Internal Fixation
PCR	Polymerase Chain Reaction
PI	Principal Investigator
SADE	Serious Adverse Device Effect
SAE	Serious Adverse Event
SARS-CoV-2	severe acute respiratory syndrome coronavirus type 2
SNCTP	Swiss National Clinical Trials Portal
SOP	Standard Operating Procedure
USADE	Unanticipated Serious Adverse Device Effect
USZ	University Hospital Zurich

INVESTIGATION SCHEDULE

Table 1: Contact with study participants and procedures accomplished at each study visit

	Visit Number	0	1	2	3	4	5	x
	Visit Name	Patient enrolment	nasal decolonization	nasal decolonization	postoperative survey	nasal swab trauma subgroup	survey regular follow up 14d (+/-1)	unscheduled visits d 1-14
	Time*	min -1day	-3 minutes	+5 minutes	1 day	2 days	14 (+/-1) days	any
	Repeated event?	no	no	no	no	no	no	no
Repeated	Form name							
no	Informed consent; Inclusion / exclusion criteria	x						
no	Visit	x	x		x	x	x	x
no	Randomization		x					
no	Demographics	x						
no	Medical history	x						
yes	Survey concomitant treatment	x			x		x	x
no	Nasal swab* and microbiom data (*contains info on Intervention only in event +5 min)		x	x		x	x	
no	Survey expected side effects **				x		x	x
yes	SAE and device deficiency (templates from CTC, not part of PL)		x		x	x	x	x
no	Device deficiencies		x					
no	Study End						x	

*Study or control-Intervention = Timepoint 0

** For outpatients "Survey expected side effects" is carried out by telephone

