4.4 Safety objectives

The safety of nasal aPDT will be measured. Patients will be monitored for any untoward effects related to the nasal decolonization using aPDT.

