5.3 Safety outcomes

Standardized survey for adverse effects noted after treatment and on day 1 and day 14 (+/-1) during regular follow-up consultation after surgery. For outpatient procedures, side effects are surveyed after treatment on the first day as a telephone conversation.

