The main limitation of this design is the risk of misattributing immediate adverse effects when study intervention is combined with surgical intervention under general anesthesia. Therefore, initial survey is carried out on the first postoperative day ("Visit 2") to reduce misinterpretation of surgery related symptoms. Exclusion of nasal intubation or surgery in the nose further reduce surgery or anesthesiology related effects. With an additional more homogenous subgroup of patients after open reduction and internal fixation of midface fractures, we can reduce these influences and gain additional information in the early phase after aPDT on day 2 (day of hospital discharge). On the other hand, combining intervention and study keeps the number of lost patients to follow-up limited and therefore allows also conclusive analysis of later adverse events (till 14 days post intervention).

Population

Patients undergoing surgery in general anesthesia at Maxillofacial Surgery Department of University Hospital Zurich will be included in this study. There will be 208 patients enrolled in this study (experimental group n=104, control group n=104). The target sample size is expected to reflect the demographic characteristics of the local community in terms of age, gender, and comorbidities.

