8.1.4 Labeling and supply

All consumables are pre-labeled by the manufacturer. Since the control group receive the same application of consumable (photosensitizer formulation), no additional labeling is needed. There are no deviations from the commercial products.

The manufacturer has provided two identical medical devices and the necessary consumables to perform 1'000 interventions. Replenishment during the study is not required as only 500 participants are to be included in this study. The light source has been validated for correct performance characteristics. The single-use formulation applicator (soft swab pre-saturated with photosensitizer) has been supplied by the manufacturer via approved carriers with itemized bills of lading. All consumables are stored in a controlled, secured location at room temperature. The formulation is non-sterile and is provided in the form of individually packaged, pre-saturated swabs. The formulation is labeled according to the manufacturer's standards (see **Figure 3**).

Figure 3: Formulation applicator (pre-saturated nasal swabs)

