9.3 Procedures at each visit

9.3.1 Screening visit (Visit 0)

The screening visit takes place as part of the regular consultation hours for Oral- and Maxillofacial Surgery. Patients will be informed about the study. Informed consent will be obtained. Inclusion and exclusion criteria will be reviewed. Demographic information, patient's medical history and survey of concomitant treatments will be obtained.

9.3.2 Visit 1

The first visit will take place during preparation for surgical intervention. Patient is already under general anesthesia. Randomization takes place according to description 6.2.1.

Nasal swab + aPDT

Nasal swab test 3 minutes before the study intervention as described under 8.1.3. Administer study or control intervention as described under 8.1.1 and 8.1.2.

Nasal swab + follow up

After treatment, a second nasal swab test (5 minutes post intervention) for analysis of primary outcome will be taken.

In case of AE / SAE and/or device deficiencies the corresponding eCRF forms are recorded.

9.3.3 Visit 2

The second visit will take place on first postoperative day. The study investigator (not the same investigator who carried out the study intervention) will record the survey of concomitant treatment, survey of expected side effects and AE / SAE. In addition, scheduling of visit 3 on day 14 (+/- 1) post intervention is carried out. For outpatient procedures, visit 2 is carried out by telephone.

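### The side-effect survey is never given before the intervention and has no new-or-worsened rule, so symptoms already present, mainly in fracture patients, may be reported as adverse effects in both arms

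*Combined protocol and SAP*

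**What the plan says.** **Timing.** Section 5.3 defines the safety outcome as a "Standardized survey for adverse effects noted after treatment and on day 1 and day 14 (+/-1) during regular follow-up consultation after surgery". In Table 1 the row "Survey expected side effects" is marked at day 1, day 14 and unscheduled visits. It is blank at enrolment, at both swab times on the day of surgery and at the day-2 visit of the fracture subgroup.

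**Before the intervention.** For Visit 0, section 9.3.1 says: "Demographic information, patient's medical history and survey of concomitant treatments will be obtained". No symptom form is listed. At Visit 1 the patient is already under general anaesthesia (section 9.3.2).

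**Objective and analysis.** Section 4.4 states the aim broadly: "The safety of nasal aPDT will be measured". Section 11.4.5 plans descriptive summaries by treatment group and does not refer to symptoms before treatment.

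**Arms.** Section 8.1.4 says: "Since the control group receive the same application of consumable (photosensitizer formulation), no additional labeling is needed". Under section 8.1.2 the illuminator is also inserted in the control arm; only the light stays off.

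**Acknowledged limitation.** Section 6.1 gives as its main limitation the "risk of misattributing immediate adverse effects when study intervention is combined with surgical intervention under general anesthesia". Its answers are the day-1 survey, the exclusion of nasal intubation and nasal surgery, and a more homogeneous midface-fracture subgroup.

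**The concern.** A survey taken for the first time on the day after surgery cannot show which symptoms were there beforehand. Patients with a midface fracture may plausibly arrive with nasal complaints, and some events listed in section 3.7, such as congestion or altered smell, could be among them. None of the answers in section 6.1 removes these symptoms:

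- The day-1 survey has nothing earlier to be compared with.
- The exclusions deal with symptoms caused by anaesthesia or nasal surgery, not by the injury.
- The fracture subgroup is the one most likely to have symptoms at entry.

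At stake are the reported side-effect percentages in each arm, and the precision with which any excess due to light can be seen. A patient's state before treatment cannot be collected reliably afterwards.

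**Working it through.** **Inputs**
- Patients per arm: 104 (section 6.1).
- Reference rate within 24 h: 2,214 of 48,841 survey responses (Table 2). It comes from treatments in an industrial setting, not from surgical patients (section 3.7).
- Fracture patients per arm, *m*: 50 according to the synopsis. Section 6.2.1 gives a target of 50 without saying whether this is per arm or in total; if it is the total, *m* = 25.
- Share *q* of fracture patients who already have a surveyed symptom: no figure in the documents. Assumed range 10% to 30%.

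**Step 1: the plan's own figure.** 2,214 / 48,841 = 4.53%, which reproduces the stated 4.5%. Expected cases per arm: 0.0453 × 104 = 4.7. The plan states no precision or power for the survey; the total of 208 comes from the efficacy outcome.

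**Step 2: patients with a prior symptom, *m* × *q*.**
- *m* = 50: 0.10 × 50 = 5, to 0.30 × 50 = 15 per arm. Relative to 4.7, this is 1.1 to 3.2 times.
- *m* = 25: 0.10 × 25 = 2.5, to 0.30 × 25 = 7.5 per arm. Relative to 4.7, this is 0.5 to 1.6 times.

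**Step 3: the reported rate.** Let *d* = 0.045 be the rate of new side effects, independent of prior symptoms. If every prior symptom is reported, the rate is *d* + (*m*/104) × *q* × (1 − *d*).

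| *m* per arm | *q* | Reported rate |
|---|---|---|
| 50 | 10% | 0.045 + 0.481 × 0.10 × 0.955 = 9.1% |
| 50 | 30% | 0.045 + 0.481 × 0.30 × 0.955 = 18.3% |
| 25 | 10% | 0.045 + 0.240 × 0.10 × 0.955 = 6.8% |
| 25 | 30% | 0.045 + 0.240 × 0.30 × 0.955 = 11.4% |

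**Step 4: precision of the arm difference.** The 95% half-width is 1.96 × √(2*p*(1 − *p*)/104).
- *p* = 4.5%: 5.6 points.
- *p* = 9.1% and 18.3% (*m* = 50): 7.8 and 10.5 points.
- *p* = 6.8% and 11.4% (*m* = 25): 6.8 and 8.6 points.

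**Step 5: what the arm difference measures.** Prior symptoms contribute equally to both arms in expectation, so they create no difference. Effects of the formulation and of insertion also occur in both arms. If these caused all of a 4.5% rate, the expected difference would be 0; if the light caused all of it, 4.5 points. The contrast therefore concerns light activation only, with or without a baseline survey.

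**The case against.** Four points on the other side carry weight.

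- **Counting is not certain.** A reader might infer that prior symptoms are necessarily counted. The survey form is not in the documents, and it may ask only about new symptoms. Section 9.2.3.1 has onset and association with the device recorded for adverse events, section 7.4 treats new clinically significant findings as adverse events, and medical history is taken at Visit 0. This stands, so the wording has to be *may be counted*. But no stated rule links these records to the survey summaries. The separate analysis plan announced in section 11 could add a rule, but not a baseline that was never collected.
- **The randomised comparison is sound.** A reader might infer that it is biased. The documents do not support that: midface fracture is a randomisation stratum and the interviewers are blinded (sections 6.2.1 and 6.2.2).
- **The overlap with fracture symptoms is limited.** Table 2 classes headache and nosebleed as unexpected. Runny nose and sneezing make up (909 + 603)/2,087 = 72% of the expected effects within 24 h. This stands and is a reason for caution about the assumed 10–30%.
- **A baseline does not settle the safety of the whole treatment.** A reader might infer that change within patients would isolate formulation and insertion effects. It would not, because anaesthesia and surgery fall between any preoperative survey and day 1. New surgical symptoms would also remain, so the 5.6-point half-width is a best case. Nor does the point extend to efficacy: there the light-only contrast is the declared question (sections 4.2 and 11.1), and a baseline swab is taken.

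**Conclusion.** The point holds as a weakness of the descriptive safety rates. The survey has no administration before the intervention and its analysis has no new-or-worsened rule, so existing symptoms, mainly in the fracture stratum, may appear as adverse effects in both arms. Under the assumed 10–30% prevalence, the reported rate would be about 9–18% with 50 fracture patients per arm, or about 7–11% with 25, instead of 4.5%. These sizes rest on three things that the documents do not settle: the prevalence, the size of the stratum, and whether the survey picks up symptoms that are not new. The 4.5% itself comes from a different population.

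The comparison between arms is not biased; it loses precision. The safety of formulation, insertion and light together is not identified by this design, and adding a baseline survey does not change that. The change is worth making because it is cheap and cannot be made for a patient after treatment.

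**What to change.** 1. **Table 1 and section 9.3:** give the same survey form once before the intervention, either at Visit 0 or at the admission contact on the day of surgery, when consent is updated (section 6.1). The admission contact is closer to treatment and, under section 9.3.2, precedes randomisation.
2. **Sections 5.3 and 11.4.5:** report items that are newly present or worse than that baseline at day 1 and at day 14, by arm and within the surgery-type strata.
3. **Section 11.4.5 and the report:** state that the between-arm safety conclusion concerns light activation only, and that the baseline does not separate formulation or insertion effects from surgical effects.
4. **Synopsis and section 6.2.1:** clarify whether the fracture subgroup is to have 50 patients per arm or 50 in total.

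Cost: a few minutes per patient, one extra eCRF instance and a few sentences of text. No additional visit or procedure is needed.

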6.2 Methods for minimizing bias

The design as randomized controlled trial allows minimizing bias by disinfecting effects of chlorhexidine gluconate or unactuated methylene blue photosensitizer. In addition, a control group reduces influence due to concomitant therapies such as nasal rinse or antibiotic treatments as part of the standard postoperative protocol.

Exclusion of nasal intubation and nose surgery reduces misinterpretation of surgery or anesthesiology related side effects (nose bleeding, itchy nose, pain).

Third visit for midface trauma subgroup on day 2 (normally day of hospital discharge) helps to reduce intubation related changes and provide a low number of patients lost for follow-up.

Combining the fourth survey "Visit 4" with the regular 14 day follow up after surgery should cause a significant reduction of lost patients for follow-up.

There is no reasonable likelihood of introducing bias into the determination of colonization status. Clinical care and routine microbial analysis will be provided and conducted as usual with no change to the clinical pathway.

6.2.1 Randomization

Randomization will be performed in REDCap. Clinicians conducting the postoperative surveys will not have access to the eCRF form with the randomization result and therefore be blinded against the treatment group.

Stratified block randomization with variable block size for type of surgery (osteosynthesis removal; open reduction and internal fixation of midface fractures vs other).

Explanation for stratification:

Removal of osteosynthesis material rarely requires any of the under 8.6 mentioned concomitant treatments. In addition, the patients are generally younger and have less comorbidities. Therefore, a stratified randomization to intervention and control group is justified. The second stratification for patients undergoing open reduction and internal fixation of midface fractures is necessary to build the subgroup (target size n=50) with additional swab on day 2 (day of hospital discharge). Also, this patient collective is more consistent in duration of surgery and concomitant treatment.

6.2.2 Blinding procedures

Due to study intervention during general anesthesia blinding of study participants is fulfilled. The investigator conducting the postoperative survey (day 1 and 14 (+/- 1)) is not the same as conducting the study intervention during surgery. Therefore, the examiner is also blinded.

Microbiological analysis is carried out via routine diagnostics without need for specific blinding.

7. CLINICAL INVESTIGATION POPULATION

7.1 Eligibility criteria

Subjects who meet all the following inclusion criteria are eligible for the investigation:

- Provision of a signed and dated informed consent form
- Stated willingness to comply with all study procedures and availability for the duration of the study
- Male or female ≥ 18 years of age
- surgical intervention in general anesthesia at the department of oral and maxillofacial surgery of University Hospital Zurich

The presence of any of the following exclusion criteria will lead to the exclusion of the subject:

- inability to tolerate insertion of the light illuminator or the photosensitizer applicator due to anatomic variations (size, shape of oro-nasal region) or disease
- inability to follow the procedure of the investigation, e.g., due to language problems or psychological disorders of the subject
- known allergic reactions to components of the nasal decolonization treatment, including methylene blue or chlorhexidine gluconate
- planned surgery in the nasal cavity
- necessary nasal intubation for surgical intervention
- vulnerable persons (subjects incapable of judgment or subjects under tutelage)
- Pregnant or breastfeeding women

7.2 Recruitment and screening

Recruiting will take place during consultation at Department for Oral and Maxillofacial surgery at University Hospital Zürich. Patients will be asked and informed about the study in case of an indication for surgery in general anesthesia.

The study does not require long-term participation. Subjects do not receive payment or compensation.

7.3 Assignment to investigation groups

Of the total 208 participants 104 will be randomly assigned to the experimental group and 104 to the control group. Randomization process is executed as described under 6.2.1.

7.4 Criteria for withdrawal / discontinuation of subjects

Withdrawal of subjects

If a clinically significant finding is identified after enrollment in the study (including, but not limited to changes from baseline), the principal investigator or qualified designee will determine if any change in participant management is necessary. Any new clinically significant finding will be reported as an adverse event (AE).

Participants are free to withdraw from participation in the study at any time upon request.

An investigator may exclude or withdraw a participant from the study for the following reasons:

- significant non-compliance with the study intervention due to intolerance of the nasal illumination
- if any clinical adverse event or other medical condition occurs such that continued participation in the study would not be in the best interest of the patient

The reason for the participant's discontinuation or withdrawal from the study will be recorded in the Case Report Form (CRF). Subjects who sign the informed consent form and are enrolled in the study, but do not receive the study intervention, may be replaced. Subjects who receive the study intervention and subsequently withdraw, or are withdrawn or discontinued from the study, will not be replaced.

Patients lost to follow-up

Participants are considered "lost to follow-up" if they fail to report for scheduled study visits and cannot be reached to complete all protocol-required study procedures.

The following actions will be taken if a participant fails to attend a required study visit:

- The investigator will attempt to contact the participant and reschedule the missed visit for 1 day. These contact attempts will be documented in the participant's study file.
- Should the participant continue to be unreachable, they will be considered to have withdrawn from the study with a primary reason of "lost to follow-up".

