8.4 Data collection and follow-up for withdrawn subjects

The reason for withdrawal will be noted in the CRF as described in chapter 7.4. In case of withdrawal, no further data will be collected. If the reason for the withdrawal is any problem related to the safety or performance of the medical device, the principal investigator will ask the subject for permission to follow their status and condition outside of the study. The data collected at the time of withdrawal will be used for statistical analysis in accordance with Art. 3 Abs. b ClinO-MD and subsequently anonymized. All biological material will be destroyed after evaluation.

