9.2.4 Assessments in subjects who prematurely stop the investigation

The reason for withdrawal will be noted in the eCRF as described in chapter 7.4. In case of withdrawal, no further data will be collected. If the reason for the withdrawal is problems related to the safety or performance of the medical device, the principal investigator will ask the subject for permission to follow their status and condition outside of the investigation. The data collected at the time of withdrawal will be used for statistical analysis in accordance with Art. 3 Abs. b ClinO-MD and subsequently anonymized. All biological material will be destroyed after evaluation.

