11.5 Handling of missing data and drop-outs

For the primary outcome, which is measured 5 min after aPDT, we do not expect any missing values since loss to follow-up is very unlikely. We plan to do complete case analyses of the primary and the secondary outcomes. Should more than 5 % of the primary outcome measurements be missing, we would use multiple imputation of the missing primary outcome data. The final number of imputations per missing value would be determined by the fraction of missing information (21).

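### An investigator may withdraw a patient from the whole study when an adverse event makes staying in it against the patient's interest; study data then stop, although after the single session only surveys and swabs remain

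*Combined protocol and SAP*

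**What the plan says.** Section 7.4 sets the rule: "An investigator may exclude or withdraw a participant from the study for the following reasons". Two grounds follow. One is "significant non-compliance with the study intervention due to intolerance of the nasal illumination". The other applies "if any clinical adverse event or other medical condition occurs such that continued participation in the study would not be in the best interest" (meaning the patient's). The same section foresees withdrawal after the intervention, because it says that treated patients who are then withdrawn are not replaced.

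The consequence for data stands in 8.4 and is repeated in 9.2.4: "In case of withdrawal, no further data will be collected". There is one exception. If the reason is a problem with the safety or performance of the device, "the principal investigator will ask the subject for permission to follow their status and condition outside of the investigation". What was gathered before is retained: "The data collected at the time of withdrawal will be used for statistical analysis".

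Section 8.2 covers removing the device during the session. No section says that a patient whose session is stopped, or who has an adverse event, stays in follow-up.

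On missing data, 11.5 states: "We plan to do complete case analyses of the primary and the secondary outcomes". If more than 5% of primary outcome values are missing, "we would use multiple imputation of the missing primary outcome data". No imputation is offered for the day-2 or day-14 scores.

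**The concern.** In a trial with continuing treatment, withdrawing a patient for an adverse event at least ends the exposure. Here the exposure is one 14-minute sequence during preparation for surgery (8.1.1, 8.1.2, 9.3.2). Once it is over, only observation is left: the day-1 and day-14 surveys, the day-14 swab and, for the midface-fracture subgroup, the day-2 swab. The rule does not separate stopping the intervention from leaving the study, so a withdrawal after the session can only remove outcome data.

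The loss is selective, because the patients who can be removed in this way are those with an event or a medical condition. Section 6.1 argues that combining the study with surgery keeps losses low and so supports an analysis of later adverse events up to 14 days. The withdrawal rule pulls the other way. At stake are the day-14 safety survey, the status of an ongoing event up to that visit, and the day-2 and day-14 secondary swabs.

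**Working it through.** **The rules, followed through for one patient**

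1. The session is completed and the 5-minute swab is taken under the same anaesthesia (9.3.2). The primary outcome is in hand.
2. An event occurs afterwards, and the investigator judges continued participation not to be in the patient's best interest (7.4).
3. The patient leaves the study and no more study data are collected (8.4, 9.2.4).
4. Lost: whichever of the day-1 survey, day-2 swab (subgroup), day-14 survey and day-14 swab are still to come.
5. Kept: everything up to withdrawal, including the event that led to it.
6. Section 10.3 records adverse events from consent to the last procedure required by the plan and asks for no safety follow-up beyond it. The loss is therefore limited to the period up to the day-14 visit. Section 10.3 does not say whether recording goes on after withdrawal; 8.4 and 9.2.4 say that it stops.

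**The plan's own figures (11.2)**

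Inputs: difference 3, SD 6, two-sided 5%, power 90%.

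- Per arm: 2 × (1.960 + 1.282)² × 6² / 3² = 84.1, so 85 per arm and 170 in total. This agrees with the plan.
- 170 / 0.864 = 196.8, rounded up to the even number 198. This agrees.
- 198 × 1.05 = 207.9, so 208; dividing instead, 198 / 0.95 = 208.4. The stated 208 is within rounding.

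These figures size the 5-minute primary outcome. They give no rate of withdrawal for adverse events.

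**Size at day 14**

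From the documents: 104 per arm (7.3), SD 6 and planned difference 3 (11.2). Assumed, because the documents give no figure: 0 to 3 such withdrawals, all in one arm; withdrawn patients differ from completers by 3 to 6 points; the day-14 SD is also 6.

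- Share of that arm's day-14 visits lost: 1/104 = 0.96%; 3/104 = 2.88%.
- Shift of the complete-case arm mean = k × d / 104, where k is the number withdrawn and d their difference from completers. With at least one withdrawal it runs from 1 × 3 / 104 = 0.029 to 3 × 6 / 104 = 0.173 points. Divided by 6, that is 0.005 to 0.029 SD.
- Withdrawals in one arm needed for a shift of 0.3 points (a tenth of the planned primary difference): 0.3 × 104 / 6 = 5.2, so 6 patients at 6 points; 0.3 × 104 / 3 = 10.4, so 11 patients at 3 points.
- Standard error of the difference: 6 × √(1/104 + 1/104) = 0.832 with nobody lost; 6 × √(1/104 + 1/101) = 0.838 with three lost from one arm.

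**Size at day 2**

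With about 50 per arm in the midface subgroup (Synopsis), each withdrawn patient is 1/50 = 2% of the arm and shifts its mean by 3/50 = 0.06 to 6/50 = 0.12 points.

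The mean shift only indicates scale. The planned analyses are a Wilcoxon-Mann-Whitney test and proportional odds models (11.4.2, 11.4.3).

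**The case against.** The case for leaving the text alone has several sound parts.

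- **Discretion and condition.** A reader might infer that any patient with an adverse event is withdrawn. The text does not say so: the investigator may withdraw, and only if staying in would be against the patient's interest. Section 7.4 also begins with a milder step, deciding whether the patient's management needs to change and reporting the finding as an adverse event. With only surveys and swabs ahead, the condition should seldom be met. This stands.
- **A further swab can itself be unwise.** Section 3.7 notes that swabbing can in rare cases cause a nosebleed, so an investigator may have good reason to spare a patient the next one. This stands too, but it justifies omitting a swab, not ending the surveys and event recording.
- **The intolerance ground is nearly empty.** Patients are anaesthetised, and inability to tolerate insertion is already an exclusion criterion (7.1).
- **The secondary data are not wholly unprotected.** A reader might infer that nothing offsets the missing day-2 and day-14 scores. Section 11.4.3 plans a mixed-effects proportional odds model of the post-treatment scores together, which may use a withdrawn patient's earlier values. How this fits with the complete-case sentence in 11.5 is not spelled out. The model does not help the separate day-2 and day-14 comparisons or the safety survey.
- **Event documentation.** Sections 9.2.3.1 and 10.3 ask for the duration and resolution of adverse events, and device-related withdrawals have a follow-up route. That route needs permission, lies outside the study and restores no survey or swab.
- **Blinding.** Patients and survey examiners are blinded, and both arms receive the same formulation and illuminator insertion. Putting all losses in one arm is therefore an unfavourable assumption.

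Together these points make the expected effect small. They do not remove the rule itself, which ends study data collection in patients with events when there is no treatment left to stop.

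**Conclusion.** The point holds as a minor one. Sections 7.4, 8.4 and 9.2.4 together allow selective loss of follow-up in patients with an event or medical condition, with no study treatment left to stop, and this runs against the purpose stated in 6.1.

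Its reach is limited to the remaining surveys, adverse-event status up to day 14, and the day-2 and day-14 secondary swabs. A reader might infer that the safety analysis loses the adverse events themselves, or that the main result is biased. The documents support neither. The triggering event and all earlier data are kept, and the primary swab comes 5 minutes after the session, so it is lost only if withdrawal comes before it.

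The number of such withdrawals is unknown and probably small. Under the assumed 0 to 3 in one arm, at most 2.9% of that arm's day-14 visits are missing and its mean score moves by at most 0.17 points (0.03 SD), with almost no loss of precision. A shift of 0.3 points would take 6 to 11 withdrawals in one arm. All of this rests on the assumed numbers and differences, not on data in the plan. The reason to act is that the change costs little.

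**What to change.** Amend 7.4, 8.4 and 9.2.4 to say:

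- An adverse event or a stopped session leads to stopping the device, or to omitting the particular procedure judged medically unwise (for example, a further swab after a nosebleed), with the reason recorded.
- The patient otherwise stays in the planned surveys, adverse-event recording and swabs up to day 14, unless they withdraw consent.

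The device-removal rule in 8.2, the patient's right to withdraw and the end of the recording period in 10.3 stay as they are. No visit is added, and no follow-up to resolution is required.

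The cost is a short amendment, possibly needing ethics committee approval under 2.9, and a few more records to complete. Visit 4 is already combined with the routine postoperative check, so most of these patients would attend anyway.
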